## Title:

Randomized Open Label study of Standard of Care Plus an Angiotensin II Receptor Blocker Compared to Standard of Care Alone to Minimize the Progression to Respiratory Failure in SARS-CoV-2 Infection

#### Primary Objective:

To identify whether or not Angiotensin Receptor Blockers (ARB) can halt the progression to respiratory failure requiring transfer into the intensive care unit (ICU) and mechanical ventilation in subjects with mild to moderate hypoxia due to COVID-19.

#### Secondary Objectives:

- To identify whether or not the use of Angiotensin Receptor Blockers (ARB) in mild to moderate COVID-19 subjects decreases the transfer from a non-ICU bed to an ICU bed.
- 2. To identify whether adding an ARB to the standard of care (SOC) for mild to moderate disease will reduce days requiring oxygen therapy.

**Hypothesis:** We hypothesize that the addition of an ARB will be beneficial in abating acute lung injury in subjects in early stages of SARSCoV-2 induced hypoxia. This abatement may decrease utilization of high-level ICU services including mechanical ventilation.

**Background:** The Coronavirus has been a known pathogen in animals since the early 1970's that resulted in gastrointestinal symptoms. Bats have been identified as the main carrier and cats have been identified as the primary means of transmission to other animals. In late 2019, the Coronavirus evolved to infect the human respiratory system (SARS-CoV-2) as seen in the outbreak in Wuhan, China. The World Health Organization named the SARS-CoV-2 epidemic COVID-19.

The current mortality rate (17MAR2020) is not well described because of the shortage of laboratory testing assays worldwide. Using WHO data on the cumulative number of deaths to March 1, 2020, mortality rates would be 5.6% (95% CI 5.4–5.8) for China and 15.2% (12.5–17.9) outside of China (Baud et al. Lancet Inf Dis; Mar, 12, 2020, https://doi.org/10.1016/ S1473-3099(20)30195-X).

At this moment (17MAR2020), grave concerns are raised about the ability of the US healthcare system to handle the demand of subjects affected by the COVID-19 pandemic. Specifically, there is concern raised by the ability to handle sick subjects and those requiring mechanical ventilation. There are an estimated 160,000 ventilators in the US. Therefore, if only 5% of the 320 million US population were infected with COVID-19, and only 2% of those required ventilation, surge capacity to provide this lifesaving supportive care would be overwhelmed.

Therefore, while the spread of virus continues to escalate logarithmically, the ability to abort subjects away from the path of acute lung injury requiring mechanical ventilation would be a huge service to healthcare. The average time from hypoxia to mechanical ventilation is nine days. Theoretically, the opportunity to effectively intervene with an ARB is soon after admission for hypoxia induced by SARS-CoV-2 and many days prior to Acute Respiratory Distress Syndrome (ARDS).

To date (17MAR2020), there have been very few human studies analyzing the effects of utilizing ARBs in the critical care setting where subjects have confirmed COVID-19 infection. The COVID-19 epidemic has already claimed more human lives than SARS and MERS combined (WHO website MAR-2020). The majority of fatalities from COVID-19 have resulted from respiratory failure.

Data has accumulated since the 2002 SARS epidemic that use of angiotensin receptor blockers may be beneficial in reducing SARS-induced respiratory failure, as summarized recently (Gurwitz, *Drug Dev Res* 04MAR2020).

It is currently believed that 80% of COVID-19 subjects will require no medical treatment, 15% will require non-ICU medical care, and 5% may require ICU admission. The goal of this study is to decrease the rate of subjects requiring ICU hospitalization and decrease the demand for mechanical ventilation.

ARBs may prevent respiratory complications for two reasons. First, ARBs compete with the coronavirus's binding site in the lung. That, in turn, has been shown to decrease the damage to the lung. Second, the ARBs decrease the inflammatory response in the lung that the coronavirus causes. By these two mechanisms, the ARBs decrease the lung damage and allows the body (host) to effectively and naturally fight against the virus.

## Number of Subjects: 200

## Inclusion Criteria:

- 1. Confirmed COVID-19 positive test result.
- Mild to moderate respiratory symptoms of COVID-19. Systolic blood pressure ≥ 100 mmHg.
- 3. Screen within 3 days of a positive COVID-19 test.
- 4. Age 18 years old.
- 5. Access to a phone in the hospital room or an electronic device that is capable of receiving phone or video calls.
- 6. Able to read/write/speak English or Spanish fluently.
- **7.** Subjects must have the capacity to provide consent or an appropriate LAR to provide informed consent
- 8. Negative pregnancy test for women of childbearing potential and subject is randomized to the study arm.

3

## **Exclusion Criteria:**

- 1. Severe allergy to any ARB, including angioedema and ACE inhibitor-induced angioedema
- 2. In the intensive care unit at screening.
- 3. Home meds include any kind of ACE inhibitor or ARB
- 4. Acute Kidney Injury (50% reduction in GFR from baseline at admission to any time during treatment in the study treatment arm)
- 5. Hyperkalemia >5.0 mmol/L at baseline or any time during treatment in the study treatment arm
- 6. Creatinine Clearance < 30 ml/min at baseline or any time during treatment in the study treatment arm

Age of Subjects: >18 yrs of age

Gender of Subjects: Either male or female

Racial and Ethnic Origin: Non-specific

Vulnerable Subjects: Hospitalized subjects

**Study Design:** Investigator initiated, open label, multicenter, two arm, randomized study to compare the impact of adding an ARB to the Standard of Care (SOC) to the SOC without an ARB. Randomization ratio will be 1:1.

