- ii. If feasible, the subject/LAR or hospital staff or CRC (if on a video call) will take a picture of the informed consent document signature pages to be saved with the copy of the consent signed by the CRC in the study records. If this is not feasible, the CRC will sign the consent and the witness and CRC will provide a dated attestation to be saved in the study records confirming that the subject/LAR agreed to participate in the study and signed the informed consent. The CRC will email the participant a copy of the consent that the CRC signed, including the witness and CRC attestation (if applicable). The CRC will also email the participant the photograph of the signature pages that the participant signed, if pictures were taken.
- c. If feasible, the LAR may be consented in person in a private setting by the CRC.
- The designated research team member will randomize the subject. The randomization will be computer generated using this website in blocks of 4 (https://www.sealedenvelope.com/simple-randomiser/v1/lists).
- 6. If the subject is randomized to the "study arm", then the Research Pharmacy will enter in the order for the chosen ARB starting dose and will not charge the subject. If the subject is randomized to the SOC arm, there is no additional work to be completed by the Research Pharmacy.
- 7. If the subject is randomized to the "study arm" and already on established antihypertensive therapy other than ACE inhibitors or ARB (which would be exclusionary), it will be up to the treating physician's discretion to hold or reduce the dose of this treatment(s) in order to allow tolerability of ARB intervention depending on the blood pressure.
- If the subject is randomized to the "study arm" a pregnancy test will be ordered as necessary for subjects of childbearing potential who have passed all the other screening criteria.
  - a. Dosing Schemata LOSARTAN is the first choice of ARB in this study and will continue based on availability. ARB alternatives are listed below: 10 days of treatment with losartan
    - i. Dose 1 and 2\*: Losartan 12.5mg PO BID for all subjects. The first AM dose can be given up to 1:00pm on Day 1.
    - ii. Dose 3 and 4 :
      - PI or delegee has the option to increase losartan dose to 25mg PO BID for subjects with a calculated creatinine clearance of >40ml/min provided the clinician is confident that the subject will

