## Hold Parameters for Study Arm subjects on ARB:

- Hold dose for SBP <100, re-check SBP in 10 min. If SBP remains <100, hold dose and call MD.
- 2. Hold dose and call MD, if potassium level increases >5.0.
- 3. Hold dose and call MD, if creatinine clearance drops below 30ml/min during treatment.

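### Some eligibility criteria apply only after randomisation and only in the ARB arm, the stated consequences conflict, and no analysis population says whether these subjects stay in the primary comparison

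*Combined protocol and SAP*

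**What the plan says.** **Eligibility.** Three exclusion criteria reach into the treatment period of one arm:

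- Item 4: "Acute Kidney Injury (50% reduction in GFR from baseline at admission to any time during treatment in the study treatment arm"
- Item 5: "Hyperkalemia >5.0 mmol/L at baseline or any time during treatment in the study treatment arm"
- Item 6: "Creatinine Clearance < 30 ml/min at baseline or any time during treatment in the study treatment arm"

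The baseline parts of items 5 and 6 apply to everyone at prescreening and are not at issue. Inclusion item 8 reads "Negative pregnancy test for women of childbearing potential and subject is randomized to the study arm". Procedures and Study Visits agrees with it: for a subject randomised to the study arm, "a pregnancy test will be ordered as necessary for subjects of childbearing potential who have passed all the other screening criteria".

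**Consequences elsewhere.** The Hold Parameters, given once in the main text and again under Protection Against Risks, say "Hold dose and call MD, if potassium level increases >5.0" and "Hold dose and call MD, if creatinine clearance drops below 30ml/min during treatment". The discontinuation parameters, also given twice, stop the ARB when GFR falls by half. Other protections against risks goes further and takes subjects with acute renal impairment on study treatment out of the study. The same section says that data capture carries on to discharge when treatment stops early.

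**Analysis.** Data Analysis names chi-square, Fisher and t-tests. It names no analysis population, no intention-to-treat rule, and no handling of excluded or withdrawn subjects.

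**The concern.** An exclusion that can be met only after allocation, and only in one arm, is not an eligibility criterion. It is a rule for removing randomised subjects selectively. The events concerned (renal impairment, raised potassium, low clearance) may be related both to the drug and to how ill the subject is. If such subjects leave the ARB arm while similar subjects remain in the SOC arm, the comparison of ventilation and ICU transfer no longer rests on randomisation.

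The direction depends on who is lost. Dropping subjects with above-average ventilation risk flatters the ARB, and dropping subjects with below-average risk works against it. Counting lost subjects as not ventilated flatters the ARB in either case. Renal withdrawal would favour the ARB under the first or last of these conditions. For potassium, clearance and pregnancy the direction is not established. The trial is also open label, so an unstated population leaves the choice open until the results by arm are known.

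**Working it through.** **Step 1: set the passages side by side.**

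| On-study finding | Exclusion or Inclusion Criteria | Hold Parameters | Discontinuation parameters | Other protections against risks |
|---|---|---|---|---|
| GFR down 50% | exclude (ARB arm) | not listed | stop ARB | withdraw from the study |
| Potassium >5.0 | exclude (ARB arm) | hold dose | not listed | no mandatory withdrawal |
| Clearance <30 ml/min | exclude (ARB arm) | hold dose | not listed | no mandatory withdrawal |
| Positive pregnancy test | ineligible (ARB arm only) | not listed | not listed | not listed |

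A held dose implies that the subject remains in the trial, and an exclusion implies the opposite. Only renal impairment carries an explicit mandatory withdrawal. That sentence names no arm, but it is tied to the period of study treatment and to whether the ARB is the cause, so it reads as an ARB-arm rule.

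**Step 2: inputs.** The protocol gives 200 subjects at 1:1, so 100 per arm. The figure of 200 cannot be reproduced, because no alpha, power, event rate or effect size is given; it is not disputed here. Everything else below is assumed:

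- no true ARB effect and one binary outcome
- base risk *p* = 0.20 in both arms
- a fraction *f* of the ARB arm affected, with ventilation risk *r* after the event (the drug already stops at ventilation, so only events that come first matter)
- two-sided 0.05, with exact enumeration over two binomials and rejections counted only when they favour the ARB

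**Step 3: affected subjects dropped.** The ARB arm has 100(1 − *f*) subjects at risk *q* = (*p* − *f r*)/(1 − *f*). For *f* = 0.10 and *r* = 0.60, *q* = (0.20 − 0.06)/0.90 = 0.156, and the risk ratio is 0.156/0.20 = 0.78.

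**Step 4: affected subjects counted as non-events.** The ARB arm keeps 100 subjects at *q* = *p* − *f r*. For the same inputs, *q* = 0.20 − 0.06 = 0.14, and the risk ratio is 0.70.

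Results for *f* = 0.10:

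| *r* | Dropped: *q* | RR | False pro-ARB finding, pooled z (Fisher) | Non-events: *q* | RR | False pro-ARB finding, pooled z (Fisher) |
|---|---|---|---|---|---|---|
| 0.10 | 0.211 | 1.06 | 1.6% (1.3%) | 0.19 | 0.95 | 3.8% (2.5%) |
| 0.20 | 0.200 | 1.00 | 2.5% (2.1%) | 0.18 | 0.90 | 5.6% (3.8%) |
| 0.30 | 0.189 | 0.94 | 3.9% (3.2%) | 0.17 | 0.85 | 8.0% (5.6%) |
| 0.60 | 0.156 | 0.78 | 12.2% (10.6%) | 0.14 | 0.70 | 20.6% (15.7%) |

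**Step 5: range, affected subjects dropped.**

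- With *f* from 0.05 to 0.15, RR runs from 1.03 to 1.09 at *r* = 0.10, and from 0.89 to 0.65 at *r* = 0.60.
- With *f* from 0.01 to 0.03 at *r* = 0.60, RR is 0.98 to 0.94 and total two-sided error is 5.2% to 5.5%.
- Suppose instead that those removed have *k* times the risk of those kept, so *q* = *p*/(1 − *f* + *f k*). At *p* = 0.20 and *f* = 0.10, *k* = 2 gives 0.20/1.10 = 0.182 (RR 0.91, false pro-ARB finding 5.0%), and *k* = 3 gives 0.20/1.20 = 0.167 (RR 0.83, 8.5%).
- Over *p* = 0.10 to 0.30, *f* = 0.05 to 0.15 and *k* = 2 to 3, RR is 0.95 to 0.77 and two-sided error is 5.1% to 18.3%.

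**Step 6: everyone analysed as randomised.** Both arms then have expected risk 0.20, this bias is zero, and two-sided error is about 5%.

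**The case against.** The strongest reply is that little data need be lost. Data capture continues to discharge after early stopping, outcomes come from the electronic record, and potassium and clearance events lead to a hold. On this reading the exclusion list only repeats treatment rules loosely, and the real conflict is one withdrawal sentence against the data-collection sentence beside it. This narrows the likely loss but does not remove the problem. Stopping treatment and withdrawing from the study are different things, the first sentence does not clearly cover the second, and data that are collected need not be analysed.

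It is also fair to say that the large figures sit at an extreme. At *f* = 0.10 and *r* = 0.60, those dropped have 0.60/0.156, or about 3.9 times, the risk of those kept. At 1% to 3% affected the effect is slight. No passage proposes counting withdrawn subjects as non-events, and the ARB-arm reading of the renal withdrawal is an inference. All of this stands, and it limits the claim to a risk of unknown size.

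Finally, the step numbering in Procedures and Study Visits is broken in the text available. That the pregnancy test is listed after the step in which, for the study arm, "then the Research Pharmacy will enter in the order for the chosen ARB starting dose and will not charge the subject" is therefore weak evidence of sequence. The point does not need it: the test is conditional on allocation in its own wording.

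**Conclusion.** The concern holds and should be fixed before the analysis can be relied on. That eligibility depends on the allocated arm, that the passages conflict, and that no analysis population is defined are all matters of text. Loss of ARB subjects from the primary comparison is a risk the plan permits, not something it states. Under the assumed inputs, the bias can be nil, slightly against the ARB (RR up to 1.09), or large in its favour (RR down to 0.65 if dropped with 15% affected). The documents contain no event rates that would narrow this range.

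**What to change.** 1. Apply every eligibility criterion to all subjects before randomisation. Remove the on-treatment, study-arm clauses from exclusions 4 to 6 as eligibility criteria.
2. Do the pregnancy test before randomisation in every woman of childbearing potential, and delete the condition on allocation from inclusion 8.
3. Replace the withdrawal wording in Other protections against risks, and add to Data Analysis: *All randomised subjects stay in data collection until discharge and are analysed in the arm to which they were randomised (intention to treat), whether study drug is held, stopped or never started, unless consent to data collection is withdrawn.*
4. Reconcile the Exclusion Criteria, both statements of the hold and discontinuation parameters, and Other protections against risks, so that each event has one stated consequence. Which clinical action follows each event is for the investigators; no rule is proposed here.

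The cost is protocol wording, plus pregnancy tests for women then allocated to SOC (at 1:1, about twice the number now tested). Follow-up does not change, because outcomes are already taken from the electronic record to discharge. The sample size does not change either.

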- vii. Subject/LAR will have a digital copy of the signed consent accessible through DocuSign®. The subject/LAR may also request a printed copy of the signed consent to be mailed to their home address.
- viii. After the consenting process, the CRC will download an electronic copy of the consent from DocuSign® (or scan a copy of the consent if the CRC provided a wet signature). The CRC will email the subject/LAR an electronic copy of the consent and print out a copy for the subject's research binder. After this, the CRC will delete the stored copy in DocuSign®. The CRC will also delete the subject/LAR contact information stored in DocuSign®.
- b. If the subject/LAR is unable or unwilling to use DocuSign®, an impartial witness will be present during the consenting process and a paper copy of the informed consent will be signed by the subject/LAR.
  - i. Upon receiving confirmation of the subject passing prescreening, a nurse or investigator will provide a paper copy of the consent to the subject/LAR. The CRC will call the subject/LAR to assure the consent process is being conducted in a private place and manner. The CRC will also ask the subject/LAR if he or she would prefer to have the consenting process conducted via video call if this technology is available at the setting of consent. An impartial witness will be added to the phone or video call. If the subject/LAR wishes to include a significant other during the informed consent discussion, the subject/LAR may add this person to the call.
    - The CRC will review the informed consent with the subject/LAR and respond to any questions the subject may have.
    - The impartial witness will confirm that the subject's/LAR's questions have been answered.

- 3. The CRC will confirm that the subject/LAR is willing to participate in the trial and sign the informed consent document while the witness is listening on the phone.
- 4. The subject/LAR will verbally confirm that they would like to participate in the trial and that they have signed and dated the informed consent document that is in their possession.
- ii. If feasible, the subject/LAR or hospital staff or CRC (if on a video call) will take a picture of the informed consent document signature pages to be saved with the copy of the consent signed by the CRC in the study records. If this is not feasible, the CRC will sign the consent and the witness and CRC will provide a dated attestation to be saved in the study records confirming that the subject/LAR agreed to participate in the study and signed the informed consent. The CRC will email the participant a copy of the consent that the CRC signed, including the witness and CRC attestation (if applicable). The CRC will also email the participant the photograph of the signature pages that the participant signed, if pictures were taken.
- c. If feasible, the LAR may be consented in person in a private setting by the CRC.
- The designated research team member will randomize the subject. The randomization will be computer generated using this website in blocks of 4 (https://www.sealedenvelope.com/simple-randomiser/v1/lists).
- 6. If the subject is randomized to the "study arm", then the Research Pharmacy will enter in the order for the chosen ARB starting dose and will not charge the subject. If the subject is randomized to the SOC arm, there is no additional work to be completed by the Research Pharmacy.
- 7. If the subject is randomized to the "study arm" and already on established antihypertensive therapy other than ACE inhibitors or ARB (which would be exclusionary), it will be up to the treating physician's discretion to hold or reduce the dose of this treatment(s) in order to allow tolerability of ARB intervention depending on the blood pressure.
- If the subject is randomized to the "study arm" a pregnancy test will be ordered as necessary for subjects of childbearing potential who have passed all the other screening criteria.
  - a. Dosing Schemata LOSARTAN is the first choice of ARB in this study and will continue based on availability. ARB alternatives are listed below: 10 days of treatment with losartan
    - i. Dose 1 and 2\*: Losartan 12.5mg PO BID for all subjects. The first AM dose can be given up to 1:00pm on Day 1.
    - ii. Dose 3 and 4 :
      - PI or delegee has the option to increase losartan dose to 25mg PO BID for subjects with a calculated creatinine clearance of >40ml/min provided the clinician is confident that the subject will

tolerate the higher dose based on the individual trends in blood pressure, renal function and potassium levels.

- For subjects with a calculated creatinine clearance of 30-40ml/min, there is no option to increase the dose of losartan on Day 2..
- iii. Doses 5 20:
  - PI or delegee has the option to increase losartan dose to 50mg PO BID for subjects with a calculated creatinine clearance of >40ml/min provided the clinician is confident that the subject will tolerate the higher dose based on the individual trends in blood pressure, renal function and potassium levels.

\* The first AM dose of ARB may be given as late as 1300 because of the low dose. The second dose would still be given at 2100.

- 7. For subjects with a calculated creatinine clearance of 30 40ml/min, there is an option to increase the dose of losartan on Day 3 to 25mg PO BID provided the clinician is confident that the subject will tolerate the higher dose based on the individual trends in blood pressure, renal function and potassium levels.Drug Shortage Plan 1: In the event of a drug shortage for losartan, olmesartan will be given at equivalent dosages
  - a. Losartan 12.5mg PO BID = Olmesartan 2.5mg PO BID
  - b. Losartan 25mg = Olmesartan 5mg PO BID
  - c. Losartan 50mg = Olmesartan 10mg PO BID
- 8. Drug Shortage Plan 2: In the event of a drug shortage for losartan AND olmesartan, valsartan will be given at equivalent dosages
  - a. Losartan 12.5mg PO BID = Valsartan 20mg PO BID
  - b. Losartan 25mg = Valsartan 40mg PO BID
  - c. Losartan 50mg = Valsartan 80mg PO BID

